6.4 Precautionary and Prohibited Medications and Procedures

6.4.1 Prohibited Medications and Procedures

Criteria for PEG-ADA administration

PEG-ADA will be continued through marrow harvest, conditioning and cell product infusion. PEG-ADA will be stopped on day +30 post cell product infusion if the patient received busulfan and the final cell product, and does not have active infections or other major medical problems.

We will recommend restarting PEG-ADA if:

By 12 months after the cell product infusion there is any one of the following:

- a) no evidence of PBMC or erythrocyte ADA enzyme activity above baseline/pre-treatment level,
- b) no evidence of immune reconstitution (absolute # CD3 cells <200/mm³),
- c) no detectable gene-marked granulocytes by ddPCR/qPCR (<1/10,000 cells).

The patient will be put back on PEG-ADA, and be followed-up medically.

PEG-ADA **may** be re-started if:

The PI deems it in the best interest of the subject on clinical grounds e.g. multiple, serious or unresponsive infections or sub-normal immune reconstitution.

PEG-ADA **may** be re-stopped (after it has been re-started for above reasons) if:

Criteria for being off are present: no active infections, PBMC or erythrocyte ADA >baseline/pre-treatment levels, absolute CD3+ T cells counts $\geq 200/\text{mm}^3$, and peripheral blood samples are positive for vector sequences by ddPCR/qPCR.

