6.6 Rescue Medications

Rescue medications may be needed as a part of standard treatment for autologous hematopoietic stem cell transplantation. If the subjects experience fever while neutropenic, they will receive broad spectrum intravenous antimicrobials as per the guidelines at UCLA or NIH. The antimicrobials will be tailored based on clinical status and for any culture sensitivity results. Subjects will receive oral acetaminophen and/or oral/intravenous narcotics for pain that may occur

as a result of the bone marrow harvest. Subjects may have a reaction (e.g. rash, hypertension, hypotension, dyspnea) to the infusion of autologous cells for which they will be treated per the guidelines at UCLA or NIH. Patients may be placed back on PEG-ADA if they fail to achieve immune reconstitution and have unresponsive infections.

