If by 6 months after cell product infusion, there is no evidence of PBMC or erythrocyte ADA enzyme activity (over baseline/pre-treatment levels), immune reconstitution ($<200/\mu\text{L}$ absolute CD3+ T) and no detectable ADA gene-marking in granulocytes by ddPCR/qPCR ($<1/100,000$), PEG-ADA will be re-started.

Patients will be monitored for clonal expansion, once gene marking levels exceed 1% (see detailed monitoring schedule in [Appendix F](#)).

Long-term follow-up: After completion of the two years of post-treatment evaluation of this study, patients will be offered enrollment in a long-term follow-up study. We will attempt to maintain annual contact with all treated subjects and will obtain samples of peripheral blood cells and serum annually for archiving at -80°C , to be available for investigation of potential complications related to lentiviral-mediated gene transfer, e.g. to assess the presence of serum antibodies to lentiviral vector proteins, the presence of replication-competent lentivirus in peripheral blood cells or clonal dominance.

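### Protocol Sections 6.4.1 and 7.5 give two inconsistent PEG-ADA restart rules on the same three findings, so the written trigger for one component of 12-month event-free survival is not unique.

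*Protocol*

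**What the plan says.** Protocol Section 6.4.1 begins "We will recommend restarting PEG-ADA if" and continues "By 12 months after the cell product infusion there is any one of the following". The three grounds are no PBMC or erythrocyte ADA activity above the pre-treatment level, CD3 below 200/mm³, and granulocyte marking below 1/10,000 cells. It then says the patient goes back on PEG-ADA. A separate clause lets the PI restart on clinical grounds, with infections or sub-normal reconstitution as examples.

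Protocol Section 7.5 reads "If by 6 months after cell product infusion, there is no evidence of PBMC or erythrocyte ADA enzyme activity" above baseline, adds CD3 below 200/µL, and ends with "no detectable ADA gene-marking in granulocytes by ddPCR/qPCR" (below 1/100,000). The findings are joined by 'and', and a restart is then mandatory.

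Protocol Section 6.6 says patients may return to PEG-ADA "if they fail to achieve immune reconstitution and have unresponsive infections", with no time point.

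A return to PEG-ADA is an EvFS failure event in Protocol Section 4.2.1.2 and in SAP Sections 5.1 and 8.3.1.2.

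**The concern.** The restart is an investigator's decision in an open-label trial, and it is also a primary-endpoint event. What the protocol tells the investigator to do therefore partly determines how often the event occurs. A subject with CD3 below 200 at month 12 but adequate ADA activity and clear marking meets the written ground in 6.4.1 and not the one in 7.5. A site that works from 7.5 could leave that subject off PEG-ADA and still be following the protocol.

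The SAP does not cover this. Its sensitivity analyses (Section 8.3.4) run only if major protocol violations are found. With two written rules, the same non-restart can comply with one section and depart from the other. A reader of a high EvFS figure cannot tell whether any subject counted as event-free had met a written restart criterion.

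**Working it through.** **1. The two rules side by side**

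| | Section 6.4.1 | Section 7.5 |
|---|---|---|
| Time | by 12 months | by 6 months |
| ADA activity | none above baseline | none above baseline |
| CD3 | below 200/mm³ | below 200/µL (same level) |
| Granulocyte marking | below 1/10,000 | below 1/100,000 |
| Combination | any one | all, joined by 'and' |
| Force | recommended, though the following sentence puts the patient back on PEG-ADA | mandatory |

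The ADA and CD3 criteria agree. Timing, combination, marking cut-off and opening force do not. The cut-offs differ by (1/10,000)/(1/100,000) = 10. The halting rule (Section 9.9) and the individual stopping rule (Section 9.10) also use 1/10,000, so 1/100,000 appears only in 7.5.

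**2. How the criteria relate**

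Let A be no ADA activity and C be CD3 below 200. Let M4 be marking below 1/10,000 and M5 marking below 1/100,000. Section 6.4.1 is A or C or M4; Section 7.5 is A and C and M5. M5 implies M4, so at any common assessment time every subject who meets 7.5 also meets 6.4.1. The laboratory criteria are nested.

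The marking cut-off therefore does little by itself. In 7.5 it decides only when A and C both hold, and 6.4.1 is then already met. In 6.4.1 it decides only when neither A nor C holds, and 7.5 then cannot apply at either cut-off. Most of the discordance comes from any-versus-all and from timing.

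Nesting does not carry across time points. A subject could meet 7.5 at month 6 and, if left off PEG-ADA, no longer meet 6.4.1 at month 12.

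**3. The plan's own precision figures and the weight of one event**

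Protocol Section 11.4 gives half-widths of 7% at 20/20 and 12% at 19/20, defined by the two-sided 95% exact binomial interval. The limits for x successes in n are the 0.025 quantile of Beta(x, n−x+1) and the 0.975 quantile of Beta(x+1, n−x).

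- 19/20: 75.1% to 99.9%, half-width 12.4%. This matches 12%.
- 20/20: lower limit 0.025^(1/20) = 83.2%, half-width (100 − 83.2)/2 = 8.4%. The stated 7% appears only with all 5% in one tail: 0.05^(1/20) = 86.1%, half-width 7.0%. This side discrepancy does not affect the point.

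One restart moves EvFS by 1/20 = 5 points and the lower bound from 83.2% to 75.1%. At 18/20 the interval is 68.3% to 98.8%.

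**4. Any versus all: illustration only**

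The documents give no failure probability for a single criterion. Assume a common probability q, independence, and one time point and cut-off. Any-one is 1 − (1 − q)³; all-three is q³.

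- q = 1%: 3.0% versus 0.0001%
- q = 5%: 14.3% versus 0.0125%, that is 2.85 versus 0.0025 expected among 20
- q = 10%: 27.1% versus 0.1%
- q = 20%: 48.8% versus 0.8%

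If the findings always occur together, both equal q and the gap is zero. The true gap lies between zero and these values.

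**5. Timing and the 12-month cut**

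Visits have a window of 4 weeks either side (Section 8.4). SAP Section 8.3.1.2 dates an event as 12 × days/365.25. A month-12 visit held 28 days late falls 12 × 28/365.25 = 0.92 months after month 12. A restart decided there could miss 12-month EvFS, though it would count at 24 months. A restart under the 6-month rule would normally fall inside.

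**The case against.** The strongest reply is that the documents rank the texts. Section 7.1 presents Section 7 as an outline and sends the reader to Appendix B, and Appendix B sends the reader to 6.4.1 for PEG-ADA management. The rules could also form two tiers: strict and mandatory at 6 months, looser and advisory by 12. The cross-references stand as a pointer, but nothing withdraws 7.5. No tier scheme is stated, and tiers alone would not explain two numerical meanings of undetectable marking in the same cells by the same assay.

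Other parts of the reply stand in full:

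- A reader might infer that one subject could be both a failure and event-free. EvFS counts actual restarts, so each subject has one status. Only the trigger is in doubt, and the PI clause leaves room for judgement even after reconciliation.
- A reader might infer that 6.6 is a third conflicting rule. It is permissive, and it fits within the illustrative grounds of the PI clause.
- A reader might infer that results were affected. Section 2.1.6.2 reports 100% EvFS in 18 evaluable patients at 31 March 2016.
- By October 2016, 20 patients had been treated and enrolment was closed, so 12 months had passed by October 2017. The latest logged protocol version is March 2018. A text change now cannot alter conduct behind 12-month EvFS.

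**Conclusion.** The inconsistency between Sections 6.4.1 and 7.5 is in the current text and concerns timing, any-versus-all logic, marking cut-off and force. It leaves the written trigger for a component of 12-month EvFS without a unique definition. It does not make the endpoint ambiguous, and no subject is shown to have been classified differently because of it.

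The effect per restart is 5 points of EvFS at n = 20, as for any single event at that size. How many restarts the choice of rule could change cannot be determined from the documents; the any-versus-all figures rest on an assumed q and on independence.

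Severity is moderate: the correction is cheap, and it bears on patient management and on how a primary event arises. A must-fix rating is not supported.

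**What to change.** **Protocol.** Sections 6.4.1 and 7.5 must be reconciled into one consistent statement of timing, any/all logic, marking cut-off and force, and Section 6.6 aligned by cross-reference. No view is taken here on which rule is right.

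**SAP.** Add a supportive listing or count, for OTL-101 subjects only, of those who met either written set without restarting PEG-ADA. Assess each set at its own time point: month 6 for 7.5 and month 12 for 6.4.1. Fixed times matter because Protocol Section 2.3.1 expects lymphocytes to fall, and perhaps stay low for several months, after PEG-ADA is withdrawn.

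Keep this outside the comparison with the HSCT controls and do not recode EvFS. Vector marking does not apply to those controls. The GOSH data list in Appendix H has no lymphocyte subsets or ADA activity, and Duke's values come in windows of 1-8, 9-16 and 17-30 months. Counting laboratory findings as failures would penalise one arm only.

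**Cost.** One protocol clarification and one listing. ADA activity, lymphocyte subsets and vector marking are already scheduled at months 6 and 12 (Appendix B) and summarised in SAP Sections 8.3.2.4, 8.3.2.6 and 8.3.2.7. If no subject qualifies, the listing supports the primary result.

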7.6 Clinical and Laboratory Evaluations

7.6.1 Clinical and Research Laboratory Evaluations and Specimen Collection

Follow-up:

1. Hematology: hemoglobin, hematocrit, WBC count with differential, platelet count [specimen: 2mL whole blood anti-coagulated with EDTA; method: automated counter (e.g. Coulter counter, or equivalent)]
2. Biochemistry: albumin, creatinine, total bilirubin, ALT, AST, glucose (non-fasting), total protein, calcium, electrolytes, alkaline phosphatase, BUN (specimen: 1mL serum; method: automated machine)

Special Assays

1. Measurements of deoxyadenosine metabolites and ADA activity in RBC (specimen: 2mL whole blood anti-coagulated with heparin, method: per protocol in [name] lab at Duke University).

2. Measurement of ADA expression in PBMCs by ADA enzymatic assay (specimen: 4mL whole blood anti-coagulated with heparin, method: ADA enzyme research assay kit, Diazyme).
3. Determination of absolute numbers of CD3+, CD4+ and CD8+ T lymphocytes, CD19+ B lymphocytes and CD56/CD16+ NK cells (specimen: 4mL whole blood anti-coagulated with EDTA; method: flow cytometry); CD4+/CD45RA+ and CD4+/CD45RO sub-sets, if sufficient cells are obtained.
4. T cell proliferative responses to PHA, tetanus toxoid (specimen: 2-8mL whole blood anti-coagulated with heparin, method: ³H incorporation or CFSE labeling)
5. T-cell receptor excision circles (TREC): As a measure of *de novo* T lymphopoiesis, T-cell receptor excision circles (TREC) will be measured in CD3+ PBMC at serial time-points (and CD4 and CD8 + cells, if available). This assay will be performed in the Bone Marrow Lab of Great Ormond Street Hospital (GOSH) for Children, London, UK, again to provide consistency between the US and UK trials.
6. TCR V β family usage on CD3+ PBMC by flow cytometric analysis will be performed at the UCLA and NIH Clinical Immunology Labs.
7. Quantitative determination of immunoglobulin (IgG, IgA, IgM) levels (specimen: 0.5mL serum, method: per clinical laboratory)
8. Determination of specific antibodies to tetanus toxoid and phosphoribosyl phosphate (PRP) (~every 3 months if not receiving IVIg; specimen: 0.1mL serum)
9. Measurement of the frequency of cells containing the inserted ADA gene in PBMC and granulocytes, as well as MACS-sorted T cells and myeloid cells (if quantities permit) (specimen: 4mL whole blood anti-coagulated with heparin or EDTA, method: quantitative PCR or digital droplet PCR)
10. Determination of replication competent lentivirus (RCL) at baseline, 3, 6, 12, and 24 months post-infusion and archived annually thereafter (specimen: 2mL whole blood anti-coagulated with heparin; method: DNA PCR at NGVB).
11. Sample banking at baseline, 3, 6, 12, and 24 months post-infusion and annually thereafter, for possible western blot testing (WB) for RCL (specimen: 0.5mL serum, method: WB at NGVB).
12. Leukemia monitoring at baseline, and at ~6-month intervals for the first five years post-infusion, then annually for an additional 10 years (15-year total monitoring after infusion). Performed only if criteria for triggering leukemia determination are fulfilled (see monitoring plan) [specimen: 2mL whole blood anti-coagulated with heparin, method: linear amplification mediated (LAM)-PCR] (at NGVB)
13. **Integration Site Analysis:** To monitor vector integration sites, both for safety and scientific analyses, genomic DNA from PBMC at specific time-points will be analyzed using non-restrictive LAM-PCR and bioinformatic analysis at UCLA and NHGRI.

A general protocol for investigation of possible clonal proliferations that might develop as a result of insertional oncogenesis will be followed. The purposes of the protocol are to:

Provide adequate monitoring so that determination of the need for therapeutic intervention is made as expeditiously as possible;
Minimize the risk of either physical or psychological harm of unnecessary interventions, to which subjects are exposed;
Characterize any clonal proliferation events occurring in gene therapy trials;
Determine whether any clonal proliferation resulted from insertional oncogenesis;
Characterize the clonality of the normal, genetically-modified hematopoiesis after lentiviral gene therapy of HSC.

(A detailed method and protocol are discussed in [Appendix F](#) - Monitoring for Monoclonal Expansion or Leukoproliferation.)

Specimen Preparation, Handling and Shipping

Biohazard Containment

The vector supernatant will be shipped on dry ice under UN 2814 (infectious substances) and UN 1845 (dry ice) from IUPVF to UCLA and NIH. The bone marrow harvest will be performed in an Operating Room at the clinical site. These Operating Rooms meet the national standards for the Joint Commission for Accreditation of Healthcare Organizations (JCAHO) and Occupational Safety and Health Administration (OSHA). The cells will then be transported for CD34+ isolation in a closed container for processing in the Good Manufacturing Practice (GMP) suite and the UCLA Bone Marrow-Stem Cell Laboratory or in the Cell Processing Section of the Department of Transfusion Medicine (CPS, DTM) of the NIH Clinical Center. All viral transduction will be performed in the GMP suite, which has its own equipment, including a biosafety cabinet, incubator, and centrifuge, as well as negative pressure airflow. The cells will be washed of all viral particles prior to being placed in a syringe for transport and re-infusion. All needles, blood, blood products, viral products and biohazard waste will be handled, shipped, and disposed by following the rules and regulations set forth by the UCLA Office of Environmental Health and Safety and NIH IBC through recommendations from the Centers for Disease Control and Prevention and the National Institutes of Health. Universal precautions will be used when in contact with the patient. All infectious specimens will be transported using packaging mandated in the Code of Federal Regulations, 42 CFR Part 72.

Instructions for Specimen Storage

The specimens collected for RCL testing at regular time-points will be stored until the 24 month time-point results are available. If there are no detected RCL, then the samples will become the property of the principal investigator. These specimens may be disposed properly, used for research purposes, or kept in storage indefinitely. The long-term study will monitor the status of the subject to the 15-year mark. If at this time, the subject has hematopoiesis and immune function that does not require PEG-ADA replacement, they have been taken off study, or have passed away, then the back-up can be properly disposed, used for research purposes, or kept in storage indefinitely.

Specimen Shipment Preparation, Handling and Storage

The substances covered under this section include the blood specimens that will be sent to us and other labs for the follow-up laboratory evaluations. Clinical specimens (blood) will be shipped under UN 3373 Category B. All products and specimens will be packed according to IATA DGRs according to the appropriate UN category. Personnel who will perform these functions will have certification from the UCLA or NIH Biosafety Offices for shipping biological materials.

8 STUDY SCHEDULE

8.1 Screening

Obtaining signed informed consent

The principal investigator or co-investigators will invite the subject and subject's family to an informal meeting to introduce the research study. Other investigators, research nurses, the study coordinator, etc. on the study may also be present to answer questions. The subject/subject's family will be given a sample copy of the informed consent to take home and read at their leisure. The consent will have the investigator's contact information, if they have questions about the research study.

If the subject/legal representative agrees to participate, the informed consent will take place in a conference room. Before the actual consent meeting, the investigator and subject/representative(s) will have already had informal discussions about the study, and a sample copy of the consent will have been given to the subject/representative(s) to read ahead of time.

At UCLA, consent by teleconference will be obtained in some cases, if the subject and his/her legal representative(s) live outside of Los Angeles, for the benefit of the subject. If this is the case, the consent will take place in an office or conference room designated by the subject's home physician. The home physician will be present with the subject/subject's legal representative(s) during the consent by teleconference between the subject/representative(s) and investigator.

At the informed consent, the consent is reviewed sentence by sentence, with frequent determinations (at least every page) whether there are questions from the potential subject/legal representative(s)/family. Any and all questions will be answered by the investigator(s) to the best of his ability. If the subject is between 7-12 years old, he/she will be asked to read the assent form and allowed to ask questions. A child between 7-12 years old must sign the assent form in order to participate in the research study. Once permission has been given (all applicable consents signed), the screening tests to determine eligibility will be scheduled.

Screening

Screening tests will be performed within 60 days prior to enrollment. We may use test results that already exist at the time the informed consent is obtained, provided that the date of the results fall within the criteria set above.

1. Complete history and physical examination including vital signs (temperature, pulse rate, respiratory rate and blood pressure).
2. Blood tests:
 - a) Comprehensive metabolic panel (albumin, AST/ALT, alkaline phosphatase, total protein, total bilirubin, creatinine, BUN, glucose, calcium, Na⁺, K⁺, Cl⁻, CO₂)
 - b) magnesium, phosphate
 - c) CBC with differential and platelet count
 - d) INR or PT/PTT
 - e) HIV-1 and hepatitis B, hepatitis C, CMV, and parvovirus B19 by DNA PCR
 - f) Peripheral blood for cytogenetic analyses (if cytogenetic testing was not performed on cells from amniocentesis)
 - g) Pregnancy test, if female of child-bearing age
3. Urinalysis: routine urine chemistry and microscopic examination
4. Electrocardiogram (ECG)
5. Echocardiogram (Echo)
6. Chest X-ray (CXR)
7. Pulse oximetry
8. Biopsy of suspicious skin lesions
9. Confirmation of ADA deficient SCID*

* Confirmation of ADA-deficient SCID will be based upon biochemical or genetic demonstration of ADA deficiency and T lymphopenia at the time of diagnosis. The date of these results will likely be outside of the parameters set above.

8.2 Enrollment/Baseline

If subjects meet inclusion criteria and have no findings causing exclusion, then subjects will be enrolled.

Physical exam, specified blood tests, and urinalysis will be performed within 3 days of the bone marrow harvest procedure. These studies must meet the inclusion criteria to allow enrolled subjects to undergo the bone marrow harvest. Determinations of ADA enzymatic activity, erythrocyte deoxyadenosine nucleotide levels, and immune function will be performed after screening and before treatment. PBMCs and serum will be collected and banked for future RCL determination.

1. Complete physical examination including recording of height (cm), weight (kg), and vital signs (temperature, pulse rate, respiratory rate and blood pressure).
2. Blood tests:
 - a) Comprehensive metabolic panel (albumin, AST/ALT, alkaline phosphatase, total protein, total bilirubin, creatinine, BUN, glucose, calcium, Na⁺, K⁺, Cl⁻, CO₂)
 - b) Magnesium, phosphate

- c) CBC with differential and platelet count
- d) INR or PT/PTT
- e) Type and cross for 2 units PRBC
- f) Pregnancy test, if female of child-bearing age

3. Urinalysis: routine urine chemistry and microscopic examination.

The following labs must be done prior to infusion of OTL-101:

[figure not shown]
- 4. Measurements of leukocyte or erythrocyte ADA enzymatic activity and erythrocyte deoxyadenosine nucleotide levels
- 5. Measurement of immune function
 - a. Determination of absolute numbers of CD3, CD4 and CD8 T lymphocytes, CD19 B lymphocytes and CD56/CD16 NK cells.
 - b. Proliferative responses to PHA, Tetanus toxoid and *Candida*
 - c. Measurement of serum immunoglobulin levels (IgG, IgA, IgM)
 - d. Measurement of specific antibodies to tetanus, polyribosylphosphate (PRP)
- 6. PBMC and serum banking for RCL determination

